1. LIST OF ABBREVIATIONS

ADE Adverse Device Effect

AE Adverse Event

AOFAS American Orthopedic Foot & Ankle Society

CA Competent Authority
DMP Data Management Plan

EC Ethics Committee

FDA Food and Drug Administration

HA Hyaluronan / Sodium Hyaluronate / Hyaluronic Acid HIPAA Health Insurance Portability and Accountability Act

IA Intra-articular

ICF Informed Consent Form

ICH International Conference on Harmonization

IFU Instructions for Use

ISO International Organization for Standardization

ITT Intent to Treat

MedDRA Medical Dictionary for Regulatory Activities

OA Osteoarthritis

PGA Patient Global Assessment

PI Principal Investigator

PP Per Protocol

SADE Serious Adverse Device Effect

SAE Serious Adverse Event SAP Statistical Analysis Plan

SOP Standard Operating Procedure
UADE Unanticipated Adverse Device Event

USADE Unanticipated Serious Adverse Device Effect

Anika Therapeutics, Inc. Cingal 20-03

2. STUDY SYNOPSIS

T'41 -	The December Of State of a Observation Control of Contr				
Title	A Prospective Study of a Single Injection Cross-linked Sodium Hyaluronate combined				
	with Triamcinolone Hexacetonide (CINGAL®) to Provide Symptomatic Relief of Osteoarthritis of Ankle Joint				
Study	To obtain clinical data to support an expanded indication for a single injection of Cingal®				
Objective Study					
Investigational	used for the symptomatic relief of osteoarthritis in the ankle joint.				
Product	CINGAL®: A chemically cross-linked sodium hyaluronate combined with Triamcinolone Hexacetonide supplied as a 4-mL unit dose in a 5-mL glass syringe.				
Mode of	Cingal will be injected into the intraarticular (IA) space of the index ankle using an 18-21-				
Delivery	gauge needle.				
Benvery	Intra-articular injection of the index ankle joint may be conducted under fluoroscopic or				
	ultrasound guidance as required by standard of care treatment.				
Study Design	Prospective, multi-center, open label expanded indication clinical trial.				
Phase	Phase III				
Sample Size	25 subjects will be enrolled and treated.				
Study Duration	The entire study duration from first subject in to last subject out will be approximately one				
,	and half years. The enrollment phase will be approximately 12 months with a follow-up				
	phase of 6 months. Visits will be scheduled at screening, baseline, 1 month, 3 months				
	and 6 months post treatment. First patient in is expected Nov - Dec 2020.				
Inclusion	Screening Inclusion Criteria				
Criteria	1. Age 18 years or older				
	2. Body Mass Index (BMI) ≤ 35 kg/m²				
	3. Diagnosis of symptomatic osteoarthritic joint in the index ankle (Kellgren-Lawrence				
	grade I to III) to be treated with Cingal injection.				
	4. Failed conservative treatment for joint osteoarthritis.				
	5. NRS pain on walking ≥4 and ≤9 in the index ankle.				
	6. Subject must be willing to abstain from other treatments of the index ankle for the				
	duration of the study. 7. Subject is willing to discontinue all analgesics including NSAIDs, except				
	acetaminophen/paracetamol, at least seven days before the treatment injection and				
	through the completion of the study.				
	8. Subject is willing to use only acetaminophen/paracetamol (up to a maximum of 4.0				
	grams per day per the package insert) for the treatment of joint pain for the duration				
	of the study. At least forty-eight hours prior to the Baseline Visit and each follow-up				
	visit, the subject is willing to discontinue use of acetaminophen/paracetamol.				
	9. Subject is willing to maintain a stable dose of oral glucosamine and/or chondroitin				
	sulfate products throughout the study, if taken prior to signing the informed consent				
	form (ICF).				
	10. Able and willing to provide signed informed consent.				
	Screening Exclusion Criteria				
	History of hypersensitivity to any of the ingredients in the hyaluronan or entire starting.				
	corticosteroids 2. Infection or skin disease in the area of the injection site or ankle joint				
	NRS pain on walking > 3 in the contralateral ankle				
	4. NRS pain on walking > 3 in the ipsilateral knee or hip				
	5. Subject received an injection of Hyaluronic Acid (HA) and/or steroid in either ankle				
	within 6 months of signing the informed consent form (ICF). A subject will be				
	excluded if they are planning to receive an HA or steroid injection (other than the				
	study injection) in either ankle during the course of this study.				
	6. Known inflammatory or autoimmune disorders (including rheumatoid arthritis, gout),				
	or other pre-existing medical conditions that, in the opinion of the investigator, could				
	impact treatment of the index ankle or affect the ability of the subject to accurately				
	complete the study questionnaires and comply with the study requirements.				
	7. Subject is taking medications at the time of signing the ICF which could interfere				
	with the treatment procedure, healing and/or assessments. This includes but is				

- not limited to oral or injectable anticoagulant treatments, anti-aggregant platelet treatment, chronic opioid analgesics. Low dose aspirin used for cardiovascular protection is allowed if a stable regimen is maintained for the duration of the study.
- 8. Subjects who had an oral, intramuscular, intravenous, rectal suppository or topical (excluded in index ankle only) corticosteroid prior 30 days of signing the ICF are excluded. Topical corticosteroid use at any site other than the index ankle is allowed.
- 9. Significant trauma to the index ankle within 26 weeks of screening
- 10. Chronic use of narcotics or cannabis.
- 11. Ligament instability or tear in index ankle.
- 12. Chronic impingement in the index ankle requiring surgical treatment
- 13. Diagnosis of fibromyalgia
- 14. Diagnosis of osteonecrosis in index ankle
- Subject has significant varus or valgus deformity greater than 10 degrees in either knee.
- 16. Subject requires consistent use of an assistive device (e.g. wheelchair, walker, etc.) Occasional use of a cane is acceptable.
- 17. Uncontrolled diabetes with HbA1c of >7%.
- 18. Subject is a woman who is pregnant or breastfeeding at the Screening Visit or a woman of child bearing potential who refuses to use effective contraception during the course of the study.
- 19. Subject is receiving or in litigation for worker's compensation.
- 20. Otherwise determined by the investigator to be medically unsuitable for participation in this study.

Baseline Inclusion Criteria

1. NRS pain on walking ≥4 and ≤ 9 in index ankle

Baseline Exclusion Criteria

- Subject has a decrease of ≥ 2 in the NRS pain on walking from Screening to Baseline in the index ankle.
- 2. Subject has a contraindication to continue with the study treatment injection based on the visual appearance of the synovial fluid aspirate.

Criteria for Evaluation

Primary Endpoint:

 Reduction of index ankle Numerical Rating Scale (NRS) pain on walking from baseline to 6 Months post injection.

Secondary Endpoints:

- Improvement in AOFAS index from baseline to 6 months post injection.
- Improvement in Patient Global Assessment (PGA) from baseline to 6 months post injection.
- OMERACT-OARSI responder rate in the index ankle at 6 months post injection.
- Time to treatment failure
- Reduction in Medication usage from baseline to 6 months post injection.

Exploratory Endpoints

Any comparisons across timepoints (baseline to 6 months) not described in the primary or secondary endpoints including but not limited to:

Demographics

	Medical History				
	History of joint osteoarthritis				
	Rescue Medication Use				
	Treatment Failure				
	 Injection procedure Concomitant medications 				
	Non-drug therapy				
	2				
	Safety Endpoint:				
	The incidence, severity, and relationship to treatment of all Adverse Events (AE) will be collected from the first treatment injection to the 6 month assessment.				
Statistical Analysis	The primary analysis on the endpoints will be performed on the ITT (Intent to Treat) populations. All Primary and Secondary endpoints will be analyzed using the ITT population.				
	A secondary analysis will be conducted on the Per Protocol (PP) population. Since the primary endpoint is at 6 months this is all subjects who complete the 6 month assessment and do not have a major deviation in the conduct of the protocol. For all other visits, this is defined as the subjects who complete those visits according to the protocol.				
	All safety analyses will be conducted on all subjects who undergo treatment of Cingal in the ankle joint.				
Sites	Up to 10 clinical sites in EU				
Sponsor	Anika Therapeutics, Inc. [name], United States of America				
	Phone: + 1 [contact] Fax: + 1 [contact]				

3. INTRODUCTION

Osteoarthritis (OA) is the most prevalent joint disorder worldwide and is associated with significant pain and disability [1]. It is a progressive disease that can affect any joint but most often involves the weight bearing joints such as the knee. The European Project on Osteoarthritis reported on prevalence rates for knee OA in Europe and the United Kingdom (UK). For subjects aged 65-74 years, the rate of knee OA based on clinical judgment was 36.7% in Italy and 18.6 % in the UK. For subjects aged 75 years or older the rate, based on clinical judgment was 50.8% in Italy. In the Netherlands, the self-reported rate of knee OA in subjects 65-74 years was 23.6% and for subjects 75 years or older was 31.4% [2]. Because of the high prevalence of knee OA, this disease ranked as either the top or second leading cause of disability [3]. In particular, this disease accounted for more dependence on others in climbing stairs, housekeeping and walking a mile than any other disease after adjustment for age, sex and comorbidity [3].

Osteoarthritis is defined as a "heterogenous group of conditions that leads to joint symptoms and signs which are associated with defective integrity of articular cartilage in addition to related changes in the underlying bone and at the joint margins" [4]. OA is characterized by a decreased concentration of HA in synovial fluid and a slow degradation of cartilage over years [5, 6]. The decreased concentration of HA in the synovial fluid of an osteoarthritic joint is probably caused by dilution from exudation, a decreased production of hyaluronans, and increased degradation [6]. Accordingly, the average molecular weight is diminished resulting in a loss of the viscoelastic properties of the synovial fluid for which HA is responsible [5].

Corticosteroids have long been used to alleviate pain and inflammation by injecting into the intraarticular space. Commonly used corticosteroids have been triamcinolone acetonide (TA) and triamcinolone hexacetonide (TH) which have been reviewed in the literature and found to be safe and effective for short term relief of the symptoms of osteoarthritis [7]. Standard dosing for intraarticular injections to the knee for triamcinolone hexacetonide (TH) have been reported as a 1 ml injection at a concentration of 20 mg/ml which will be the proposed dose for the active control in this trial [7].

Viscosupplements are believed to restore the concentration of hyaluronans in synovial fluid, elevate the viscosity and improve the lubricating and cushioning properties of the synovial fluid to a healthier state to alleviate pain in OA [6]. HA in synovial fluid binds to chondrocytes, supporting a role for HA in healthy cartilage [5]. HA has been studied as a substance capable of restoring the normal properties of synovial fluid and cartilage, thereby reducing pain and stiffness in the osteoarthritic joints. Exogenously administered HA immediately restores the synovial fluid's viscoelastic (or rheologic) properties [6].

Bellamy et al (2006) conducted a systematic analysis of 76 single and double-blinded studies and concluded that viscosupplements are an effective treatment for OA of the knee with beneficial effects on pain, function and Patient Global Assessment from a 5 to 13 week post injection period showing a percent improvement from baseline of 28% to 54% for pain and 9% to 32% for function [8].

Because data show a delayed treatment effect of HA, Anika Therapeutics created a product, Cingal®, that could provide quicker pain relief for subjects suffering from osteoarthritis while still providing the established pain relief of an HA product. Anika chose to add a corticosteroid, triamcinolone hexacetonide (TH), that was approved in the U.S. and Europe for intra-articular use in osteoarthritis and was labeled for frequency of injection every 3-4 weeks, to a cross-linked HA product which provides pain relief of up to 26 weeks after a single injection.

Cingal® is a sterile, biocompatible, non-pyrogenic, viscoelastic, uniform white/off white opaque solution composed of molecules of HA and triamcinolone hexacetonide (TH). Cingal® is intended to treat the pain of osteoarthritis (OA) of the knee in patients who have failed to respond to conservative non-pharmacological therapy and to simple analgesics, e.g., acetaminophen. Cingal® functions as a viscoelastic supplement or a replacement for synovial fluid in human joints with short term pain relief is provided by triamcinolone hexacetonide.

Cingal® has been studied in two Phase III trials, Cingal 13-01 and Cingal 16-02, and several follow-on studies, Cingal 13-02 and Cingal 17-02 [26-29]. Cingal® studies generated a safety data base of 642 subjects treated intra-articularly with a Cingal® injection, including 94 subjects retreated with a second injection.

Hyaluronic Acid injections in non-knee synovial joints has been reported to show benefits in pain reduction and improvement in joint function. Patients with hip osteoarthritis had significantly improved Lequesne's function and reduced VAS pain at 3 and 6 months after injection (Migliore et al. *Arthritis Research & Therapy* 2009 Vol 11 No 6). A study on the use of intra-articular HA in the treatment of symptomatic osteoarthritis of the shoulder showed an improvement in VAS score of 24 points from baseline to 6-months (Silverstein et al. *Am J of Sports Medicine*, 2007, Vol 35, No. 6). The effect of a single injection of HA on patients with symptomatic ankle (talo-crural) osteoarthritis show an improvement in VAS score of 44.5 points from baseline to 3 months (Witteveen A.G.H. et al. *I Foot and Ankle Surgery* 2008 *Vol* 14 p145-152).

The goal of this study is to demonstrate the clinical improvement and safety in patients treated with Cingal for ankle osteoarthritis. Specifically, this study will provide confirmation to the safety and performance of Cingal at relieving ankle joint pain to 6 months post-treatment.

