6.5 Trial Design

This is a prospective, expanded indications multi-center, open-label study to evaluate the safety and performance of injections of Cingal for relief of pain in patients with a diagnosis of an osteoarthritic ankle joint.

The subjects in this study will be patients with a diagnosis of osteoarthritic (OA) joint who the investigator determines are appropriate candidates for treatment with a viscoelastic injection of Cingal.

Up to 25 subjects will be enrolled and treated at up to 10 investigational sites in the EU. Subject participation will last approximately 6 Months, with visits scheduled at Screening, Baseline, 1 month, 3 month and 6 months.

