9. STATISTICAL CONSIDERATIONS

9.1 Sample Size

The primary analysis will be the mean change in index ankle pain from baseline to 6 months as measured by the Numerical Rating Scale.

The hypothesis to be tested is:

 H_0 : $\mu_{DMON} = 0$ versus H_A : $\mu_{DMON} > 0$.

In this hypothesis, μ_{DMON} is the mean change in pain from baseline at 6 Months in CINGAL treated patients.

The data will be analyzed via a one sample t-test.

It is assumed that a mean change in pain from baseline of 2 points represents a clinically significant improvement with a standard deviation of 2 - 2.5 points, for 80% power and alpha of 5% then a total of 15 subjects are required. To ensure sufficient subjects are available at the 6 month follow up, it is proposed to enroll and treat at least 25 subjects which should be more than adequate to demonstrate that treatment of the study population with CINGAL would reduce joint pain at 6 months.

Single sites should not enroll and treat more than 50% of the total enrollment.

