9.2.2 Adverse Events

Subjects with AEs will be summarized with frequencies and percentages by system organ class and preferred term, severity, and relationship to investigational product/procedure. In summaries of AEs by severity and relationship to investigational product/procedure, subjects reporting multiple episodes will be counted once under the worst severity and the strongest relationship, respectively. Serious Adverse Events will also be presented by relationship to investigational product/procedure.

Adverse events occurring prior to the index treatment will not be recorded in this trial.

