3.0 Objectives

The goal of these studies is to demonstrate the clinical improvement and safety in patients treated with CINGAL for hip osteoarthritis, shoulder osteoarthritis, and ankle osteoarthritis. Specifically, this study will provide confirmation to the effectiveness and safety of CINGAL at relieving the specified joint pain to 6 months post-treatment.

PRIMARY ENDPOINT:

• Reduction of index joint Numerical Rating Scale (NRS) pain on walking from baseline to 6 Months post injection (CINGAL 20-01), joint pain from baseline to 6 Months post injection (CINGAL 20-02), and pain on walking from baseline to 6 Months post injection (CINGAL 20-01).

SECONDARY ENDPOINTS:

- Improvement in Lequesne Hip index joint from baseline to 6 months post injection. (CINGAL 20-01 only)
- Improvement in DASH score for index joint from baseline to 6 months post injection (CINGAL 20-02 only)

- Improvement in AOFAS index joint from baseline to 6 months post injection (CINGAL 20-03 only).
- Improvement in Patient Global Assessment (PGA) from baseline to 6 months post injection.
- OMERACT-OARSI responder rate in the index joint at 6 months post injection.
- Time to treatment failure
- Reduction in Medication usage from baseline to 6 months post injection.

EXPLORATORY ENDPOINTS

Any comparisons across timepoints (baseline to 6 months) not described in the primary or secondary endpoints, including but not limited to:

- Demographics
- Medical History
- History of joint osteoarthritis
- Rescue Medication Use
- Treatment Failure
- Injection procedure
- Concomitant medications
- Non-drug therapy

SAFETY ENDPOINT:

The incidence, severity, and relationship to treatment of all Adverse Events (AE) will be collected from the treatment injection to the 6 month assessment.

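### With about 25 single-arm subjects the adverse-event data can describe safety in the ankle but not confirm it, and no planned interval shows that limit

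*Protocol*

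**What the plan says.** **The aim.** Protocol section 3 states: "The goal of this study is to demonstrate the clinical improvement and safety in patients treated with Cingal for ankle osteoarthritis". The next sentence adds that "this study will provide confirmation to the safety and performance of Cingal at relieving ankle joint pain to 6 months post-treatment". SAP 3.0 has the parallel sentence: "this study will provide confirmation to the effectiveness and safety of CINGAL at relieving the specified joint pain to 6 months post-treatment".

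**The analysis.** Protocol 9.2.2 plans: "Subjects with AEs will be summarized with frequencies and percentages by system organ class and preferred term", and also by severity and relationship. SAP 4.4 likewise plans frequencies, percentages and tabulated numbers of subjects and events. Its one inferential step is a Fisher's exact test between treatment groups. Neither section assigns a confidence interval to any adverse-event rate. Protocol 9.2 and SAP 4.2 fix the level of whatever tests and intervals are produced at 5%, but do not say that adverse events get one.

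**The size.** The synopsis says "25 subjects will be enrolled and treated". Section 6.5 says "Up to 25 subjects will be enrolled and treated at up to 10 investigational sites in the EU". Section 9.1 says "it is proposed to enroll and treat at least 25 subjects". The calculation in 9.1 concerns NRS pain only.

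**The contrast.** For the OMERACT-OARSI responder rate, a proportion in at most the same number of subjects, SAP 4.1.3.4 plans exact 95% intervals by PROC FREQ with the BINOMIAL option.

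**The concern.** The study supports use of the product in a new joint, and safety stands beside pain relief in the stated goal. Words such as demonstrate and confirmation imply that the study can rule something out. No planned safety output can do that: there is no target rate, no threshold, no interval and no precision statement. The one planned test needs a comparator that this study does not have.

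What is at stake is how far the safety conclusion can reach. A percentage out of 25, and above all a zero, carries wide uncertainty. The plan shows that uncertainty for an efficacy proportion but not for the safety proportions.

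**Working it through.** **Inputs**
- Number treated: 25 (protocol synopsis, 6.5 and 9.1, with the different wordings noted above).
- Denominator: all treated subjects (protocol 9.2.3).
- Interval level: 95%, from the 5% level in protocol 9.2. The two-sided exact form is used because it matches SAP 4.1.3.4.

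**1. The plan's own figure.** Section 9.1 asks for 15 subjects: mean change 2, SD 2 to 2.5, power 80%, alpha 5%, one-sample t-test. With the noncentral t distribution (noncentrality = 2/SD × √n), the smallest n is:

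| SD | one-sided 5% | two-sided 5% |
|---|---|---|
| 2 | 8 | 10 |
| 2.25 | 10 | 12 |
| 2.5 | 12 | **15** |

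The stated 15 is reproduced with SD 2.5 and a two-sided test (power 82.1% at n = 15). It is a pain calculation. No safety rate enters it, or the step up to 25.

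**2. What zero events would leave open.** The exact (Clopper-Pearson) upper limit for 0 of n is 1 − 0.025^(1/n) two-sided, or 1 − 0.05^(1/n) one-sided at 95%.
- n = 25, two-sided: 1 − 0.025^(1/25) = 0.1372, or 13.7%
- n = 25, one-sided: 1 − 0.05^(1/25) = 0.1129, or 11.3%

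**3. Small non-zero counts.** Exact two-sided 95% limits are the 2.5% quantile of Beta(x, 26 − x) and the 97.5% quantile of Beta(x + 1, 25 − x):

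| Subjects with event | Percentage reported | Exact 95% CI |
|---|---|---|
| 1 of 25 | 4% | 0.1% to 20.4% |
| 2 of 25 | 8% | 1.0% to 26.0% |
| 3 of 25 | 12% | 2.5% to 31.2% |

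**4. Chance that an event is not seen at all.** This is (1 − p)^25:
- p = 1%: 0.99^25 = 0.778
- p = 5%: 0.95^25 = 0.277
- p = 10%: 0.90^25 = 0.072
- p = 20%: 0.80^25 = 0.004

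For scale, a 95% chance of seeing at least one case of a 1% event needs ln(0.05)/ln(0.99) = 298.07, so 299 subjects.

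**5. Sensitivity to n (zero events, two-sided 95% upper limit).**
- 24 treated: 14.2%.
- 15 followed to 6 months (an illustration, using the number that 9.1 requires): 21.8%.
- 75, if adverse events from the three joint studies under this SAP were pooled (an assumption; the SAP plans no such pooling): 4.8%.

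**6. The Fisher's test.** It compares proportions between groups. Within the ankle study there is one group, so there is no table to test. A comparison across the three joint studies, if that were meant, would not bound the event rate in the ankle.

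**The case against.** The strongest reply is that the confirmatory words are narrative and the operative text is descriptive. The safety endpoint (protocol 6.4) is the incidence, severity and relationship of events, with no hypothesis or threshold. Section 6.5 sets out to evaluate safety, and the synopsis objective is to obtain clinical data. A reader might infer that the trial has a safety test that its design fails. The documents do not support that, because no such test is specified.

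A reader might also infer that a 0% entry will be reported as proven safety. Nothing in the documents says so. Counts on a defined population let anyone work out the interval, so no data are lost and no estimate is biased.

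A third tempting reading is that the study will routinely miss very common reactions. It will not: at a true rate of 10% the chance of seeing no case is 7%, and at 20% it is 0.4%. The frequency bands in section 4.2 grade reactions to triamcinolone hexacetonide, not to Cingal, so they should not serve as the yardstick for the product.

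Finally, section 3 cites 642 subjects treated in earlier Cingal studies, and section 4.2 expects similar events in the ankle. Confirmation might then mean consistency with knee experience. That softens the point but does not remove it, because the plan neither combines those data with the ankle data nor defines consistency.

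These arguments lower the weight of the point. They leave the mismatch between the stated aim and the planned output, and the inapplicable test.

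**Conclusion.** The point holds as a low-cost improvement to analysis and wording. With 25 treated, the absence of an event is compatible with a true rate of up to 13.7% (exact two-sided 95%; 11.3% one-sided), and events with true rates of 1% or 5% would be unseen 78% or 28% of the time. Data of that precision can describe the safety of Cingal in the ankle. They cannot confirm it, and the only inferential step planned for adverse events cannot be run within this study.

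The figures assume exactly 25 subjects in the safety population, one count per subject, and no pooling with other joints or earlier studies. With fewer subjects the limit rises. The primary pain analysis is not affected.

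**What to change.** 1. **SAP 4.4, ankle study.** Replace the Fisher's test with exact (Clopper-Pearson) two-sided 95% intervals for the proportion of treated subjects with any adverse event, any related adverse event, any serious adverse event and any injection-site event. The procedure already named in SAP 4.1.3.4 can be reused.
2. **Counting rule.** Count each subject once, as protocol 9.2.2 does. SAP 4.4 includes all episodes and defines its treatment-emergent events by relatedness, so one definition of a related event must be fixed before the second interval means anything.
3. **Precision statement in the SAP and report.** Say that with 25 subjects the absence of an event does not exclude true rates up to about 14% (two-sided 95%). This sentence matters because the four aggregate intervals do not themselves cover a zero count for a single event type.
4. **Wording.** At the next amendment, state the safety aim in protocol section 3 and SAP 3.0 as describing or evaluating safety, in line with protocol 6.5.

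Cost: no extra subjects, visits or data. The SAP also serves the hip and shoulder protocols, so its revision must be scoped to the ankle study or agreed for all three. The protocol wording has to go through the amendment process in 13.3, so it is best bundled with other changes. The safety statement becomes less favourable.
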